4.1 Description of study design

The study is a phase 3, multi-center, open-label randomized study of oral asciminib versus bosutinib in patients with Chronic Myelogenous Leukemia in chronic phase (CML-CP), previously treated with 2 or more tyrosine kinase inhibitors.

The trial is designed to compare the efficacy and safety of asciminib with that of bosutinib in the treatment of patients with CML-CP having previously been treated with a minimum of two prior ATP-binding site TKIs. Patients intolerant to the most recent TKI therapy must have BCR-ABL1 ratio $> 0.1\%$ IS at screening and patients failing their most recent TKI therapy must meet the definition of treatment failure as per the 2013 ELN guidelines ([Baccarani et al 2013](#)). No more than 66 patients (approximately 30% of the overall trial population) that are intolerant to their most recent TKI therapy with BCR-ABL1 $< 1\%$ will be recruited in order to ensure that the CML third line patient population is adequately represented.

The study will also investigate secondary endpoints for efficacy, safety and PK of single-agent asciminib compared to bosutinib. Tolerability, PK, PRO and exploratory biomarker activities will also be assessed. Safety and efficacy data for patients switching to asciminib will be collected and analyzed separately.

Patients meeting all of the inclusion and none of the exclusion criteria will be randomized into one of the 2 treatment arms, based on a 2:1 randomization between the asciminib arm and the bosutinib arm.

[figure not shown]
The randomization will be stratified to ensure the study population is balanced between the arms with respect to cytogenetic response status (See [Section 7.2.1.2](#)) at screening as follows:

- Major cytogenetic response (complete or partial)
- No major cytogenetic response (minor, minimal or none)

Patients will continue to receive the assigned study treatments (asciminib or bosutinib) until the end of study treatment period as defined in [Section 4.3](#). Patients who discontinue their study treatment at any time during the study will be followed up for survival and for progression to AP/BC for up to 5 years from the date the last randomized patient receives the first dose (irrespective of treatment switch for patients failing bosutinib).

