7.1.6 Discontinuation of study treatment

Patients may voluntarily discontinue from the study treatment for any reason at any time. If a patient decides to discontinue from the study treatment, the investigator should make a reasonable effort (e.g. telephone, e-mail, letter) to understand the primary reason for this decision and record this information in the patient’s chart and on the appropriate eCRF pages. They may be considered withdrawn if they state an intention to withdraw, fail to return for visits, or become lost to follow-up for any other reason.

The investigator should discontinue study treatment for a given patient if, he/she believes that continuation would be detrimental to the patient’s well-being. Patients who discontinue study treatment should undergo an end of treatment visit.

For patients who discontinue treatment in treatment period or switch treatment period for reasons other than death, lost to follow-up, or withdrawal of consent, the patient should enter the survival follow-up phase. Survival visit assessments (survival, antineoplastic therapies, stem cell transplant and progression) should be performed every 12 weeks until documented death, lost to follow-up, withdrawal of consent or until the end of the study. This visit can be conducted by telephone.

Patients who discontinue the study treatment for an adverse event suspected to be related to study drug or an abnormal laboratory value suspected to be related to study drug must be followed as described in [Section 8](#)

Patients may also be discontinued from the study treatment if any of the following occurs:

- discovery of patient ineligibility
- errors in treatment compliance [study treatment, other prescribed or non-prescribed medications]
- missed/unscheduled/off schedule/incomplete/incorrect assessments
- major protocol deviation
- use of prohibited treatment refer to [Section 14-Appendices](#)
- any other protocol deviation that results in a significant risk to the patient’s safety

In addition to the general discontinuation criteria, the following study specific criteria will also require discontinuation of study treatment:

- In the event of detection of T315I or V299L mutations at any time the patient **must** be discontinued from the study treatment.
- In the event of a pregnancy during study, if a patient wants to pursue the pregnancy then patient **must** be discontinued from the study treatment. However, in the event of a

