spontaneous miscarriage or in the event of elective abortion, the patient is permitted to continue study treatment.

- In the event of treatment failure the patient must be discontinued from the study treatment. Patients randomized to bosutinib treatment experiencing treatment failure may switch to asciminib treatment. The following events will constitute ‘treatment failure’, and are based on the ELN criteria ([Baccarani et al 2013](#)) defining failure of a second line treatment:
 - No CHR or > 95% Ph+ metaphases at three months after initiation of therapy or thereafter
 - BCR-ABL1 ratio > 10% IS and/or > 65% Ph+ metaphases at six months after initiation of therapy or thereafter
 - BCR-ABL1 ratio > 10% IS and/or > 35% Ph+ metaphases at 12 months after initiation of therapy or thereafter
 - Loss of CHR, CCyR or PCyR at any time after initiation of therapy
 - Detection of new BCR-ABL1 mutations which potentially cause resistance to study treatment (asciminib or bosutinib) at any time after initiation of therapy
 - Confirmed loss of MMR in 2 consecutive tests ([Section 7.2.1.1](#))
 - New clonal chromosome abnormalities in Ph+ cells: CCA/Ph+: at any time after initiation of therapy
- In the event of disease progression the patient must be discontinued from the study treatment. The following events are considered disease progression.
 1. CML-related death (any death during treatment or follow-up if the principal cause of death is marked as “study indication” in the eCRF by the investigator, or if the death occurred subsequent to documented progression to AP/BC and the cause of death is reported as “unknown” or not reported by the investigator)
 2. Accelerated phase (AP) as defined by any of the following:
 - $\geq 15\%$ blasts in the peripheral blood or bone marrow aspirate, but $< 30\%$ blasts in both the peripheral blood and bone marrow aspirate
 - $\geq 30\%$ blasts plus promyelocytes in peripheral blood or bone marrow aspirate
 - $\geq 20\%$ basophils in the peripheral blood
 - Thrombocytopenia ($< 100 \times 10^9/L$) that is unrelated to therapy
 3. Blast crisis (BC) as defined by any of the following:
 - $\geq 30\%$ blasts in peripheral blood or bone marrow aspirate
 - Appearance of extramedullary involvement other than hepatosplenomegaly proven by biopsy (i.e., chloroma).

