7.2 Assessment types

7.2.1 Efficacy assessments

7.2.1.1 Molecular response

Molecular response (MR) will be assessed in all patients randomized to each treatment arm as well as in patients that switch study treatment from bosutinib to asciminib.

Levels of BCR-ABL1 transcripts will be determined by real-time quantitative PCR (RQ-PCR) testing of peripheral blood and analyzed at a central testing laboratory. Log reduction in BCR-ABL1 transcripts levels from the standardized baseline value, or the percent ratio of BCR-ABL1 transcripts versus control gene (ABL) transcripts converted to a reference standard, international scale ([Hughes and Branford 2006](#)), will be calculated for each sample.

Major molecular response and related variables are defined as the following:

- Rate of Major Molecular Response (MMR) where MMR is defined as a ≥ 3.0 log reduction in BCR-ABL1 transcripts compared to the standardized baseline equivalent to ≤ 0.1 % BCR-ABL1/ABL % by international scale as measured by RQ-PCR, confirmed by duplicate analysis of the same sample
- Time to MMR defined as the time from the date of randomization to the date of the first documented MMR,
- Duration of MMR defined as the time from the date of first documented MMR to the earliest date of loss of MMR, progression to AP or BC, or CML-related death.

Loss of MMR is defined as increase of BCR-ABL1/ABL to > 0.1% by international scale (IS) in association with a ≥ 5 -fold rise in BCR-ABL1 from the lowest value achieved on study treatment and replicated by a second analysis of the same sample. Loss of MMR must be confirmed by subsequent sample analysis within 4 to 6 weeks showing loss of MMR associated with a ≥ 5 -fold rise in BCR-ABL1 from the lowest value achieved on study treatment, unless it is associated with confirmed loss of CHR or loss of CCyR or progression to AP/BC or CML-related death. Mutational analysis will be performed at a Novartis designated laboratory by Sanger sequencing at Week 1 Day 1, upon confirmed loss of MMR and/or at end of treatment. If the result at Week 1 Day 1 is positive for a mutation, analysis will be performed every 12 weeks.

The blood samples will be taken as described in [Table 7-1](#), [Table 7-2](#) and [Table 7-3](#).

Table 7-3 Blood samples (efficacy primary endpoint)

Sample Type	Volume	Visit	Time point
Blood for BCR-ABL1 quantification by RQ-PCR	20 mL	Screening/Baseline / S-Screening/S-Baseline*	Pre-dose
	20 mL	Week 4 / S-Week 4	Pre-dose

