10.5.2 Other secondary efficacy objectives

Unless otherwise stated the FAS will be used for the analysis of all other secondary efficacy endpoints. The exceptions are using the Molecular Responder Set for duration of MMR and time to MMR, the CCyR Analysis Set for CCyR rates, and the Cytogenetic Responder Set for duration of CCyR and time to CCyR.

No statistical testing of non-key secondary efficacy endpoints will be performed, and any analysis will be considered exploratory.

[figure not shown]
Molecular Response

MMR rates at scheduled time points (except 24 and 96 weeks which have been specified as primary and key secondary endpoints) will be evaluated in a similar fashion to the primary analysis of MMR rate at 24 weeks. Patients discontinuing the randomized treatment prior to a specific time point due to any reason will be considered as non-responders for that time point.

MMR rates by scheduled time points are defined as the proportion of patients who achieve MMR at or before the specified visit, i.e. if a patient achieves an MMR but then loses it before or at the visit, he/she will still be classed as achieving MMR by that time point.

For each endpoint the rate and the associated 95% confidence interval based on the Pearson-Clopper method will be presented by treatment group. Confidence intervals for the differences in any response rates between treatment groups will be provided using the Wald method.

Statistical testing will be performed via CMH chi-square tests stratified by the randomization strata. The Mantel-Haenszel estimate of the common risk difference and the corresponding 95% confidence interval will also be provided.

Duration of MMR is defined in [Section 7.2.1.1](#) as the time between the date of the first documented MMR and the earliest date of loss of MMR, progression to AP/BC, or CML-related death for patients in the Molecular Responder Set. The time will be censored at the last molecular assessment (PCR) date while on treatment for patients who have not experienced any of the above events.

Duration of MMR will be analyzed by K-M method and presented by K-M plots. The estimated rates of patients who are still responding at various time points will also be provided using K-M method.

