Duration of CCyR is defined as the time between date of first documented CCyR and the earliest date of loss of CCyR, progression to AP/BC, or CML-related death for patients in the

Cytogenetic Responder Set. The time will be censored at the last cytogenetic assessment date on treatment for patients for whom none of the above events is reported or last PCR evaluation on treatment indicating MMR.

Duration of CCyR response will be analyzed by K-M method and presented by K-M plots. The estimated rates of patients who are still responding at various time points will also be provided using K-M method.

Treatment failure, disease progression and survival

Time to treatment failure (TTF) is defined as the time from date of randomization to an event of treatment failure. The following events will constitute ‘treatment failure’, and are based on the ELN criteria ([Baccarani et al 2013](#)) defining failure of a second line treatment adapted to include discontinuation of randomized treatment as an event:

- No CHR or > 95% Ph+ metaphases at three months after randomization or thereafter
- BCR-ABL1 ratio > 10% IS and/or > 65% Ph+ metaphases at six months after randomization or thereafter
- BCR-ABL1 ratio > 10% IS and/or > 35% Ph+ metaphases at 12 months after randomization or thereafter
- Loss of CHR, CCyR or PCyR at any time after randomization
- Detection of new BCR-ABL1 mutations which potentially cause resistance to study treatment at any time after randomization
- Confirmed loss of MMR
- New clonal chromosome abnormalities in Ph+ cells: CCA/Ph+: at any time after randomization
- Discontinuation from randomized treatment for any reason

[figure not shown]
For patients who have not reached treatment failure, their TTFs will be censored at the time of last study assessment (PCR, cytogenetic, hematologic or extramedullary) before the cut-off date.

Progression-Free-Survival (PFS) is defined as the time from the date of randomization to the earliest occurrence of documented disease progression to AP/BC or the date of death from any cause (including progressions and deaths observed during the survival follow-up period) before the cut-off date.

The time will be censored at the date of last study assessment (PCR, cytogenetic, hematologic or extramedullary) or last post-treatment follow-up for patients without event.

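### Duration of MMR and of CCyR can count progression and CML-related death after treatment stops, but event-free patients are censored on treatment, so the Kaplan-Meier curves are biased downward

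*Combined protocol and SAP*

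**What the plan says.** **Events.** Section 7.2.1.1 runs duration of MMR from first documented MMR to the "earliest date of loss of MMR, progression to AP or BC, or CML-related death", and Section 10.5.2 repeats this. Duration of CCyR in Section 10.5.2 ends at the "earliest date of loss of CCyR, progression to AP/BC, or CML-related death for patients in the" Cytogenetic Responder Set. Neither definition confines the events to the treatment period.

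**Censoring.** For MMR, the time is "censored at the last molecular assessment (PCR) date while on treatment for patients who have not experienced any of the above events". For CCyR: "The time will be censored at the last cytogenetic assessment date on treatment for patients for whom none of the above events is reported", or at the last on-treatment PCR showing MMR.

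**What can happen after treatment.** The only definition of CML-related death is in Section 7.1.6: "CML-related death (any death during treatment or follow-up if the principal cause of death is marked as" the study indication, plus deaths of unknown or unreported cause after documented AP/BC. The same section says "Survival visit assessments (survival, antineoplastic therapies, stem cell transplant and progression) should be performed every 12 weeks until documented death" or another end of follow-up. Under Section 4.1, patients who discontinue are "followed up for survival and for progression to AP/BC for up to 5 years" from the last patient's first dose. PCR, by contrast, stops with study treatment (Table 7-3).

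**Analysis.** Both durations are analysed by Kaplan-Meier, with estimated rates of continued response at various times. Section 10.5.2 makes all non-key secondary efficacy analyses exploratory.

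**The concern.** Take two responders who stop treatment on the same day while still in MMR. One never progresses, so is censored at the last on-treatment PCR. The other progresses a year later, so stays at risk for that year and then has an event. Which of them remains in the risk set after stopping is decided by what happens afterwards. Kaplan-Meier requires that being at risk at time t does not depend on events after t. Here off-treatment time enters only for patients who fail, and the curve falls too fast. The patient who fails later is also credited with response over a period in which no PCR was taken.

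At stake is the descriptive account of how durable responses are. The bias grows with the rate of stopping while in response, so if the arms stop at different rates their curves are lowered by different amounts.

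**Working it through.** The plan states no figure for either duration endpoint, so there is none to reproduce. The check has three parts.

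**1. Event and censoring windows side by side**

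| Endpoint | Events after treatment stops | Event-free patients followed to |
|---|---|---|
| Duration of MMR | Not excluded; CML-related death in follow-up included by definition | Last on-treatment PCR |
| Duration of CCyR | Same | Last on-treatment cytogenetic assessment, or PCR in MMR |
| PFS | Included explicitly | Last study assessment or last post-treatment follow-up |

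Only PFS uses follow-up for both events and censoring.

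**2. Hand example**

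Twenty responders, time in weeks from first MMR: 10 stay on treatment event-free to week 144, 8 stop at week 48 and never have an event, and 2 stop at week 48 and progress at week 96. Kaplan-Meier estimate at week 100:

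- Rule as written: 8 are censored at week 48, so 10 + 2 = 12 are at risk at week 96 with 2 events. 1 - 2/12 = 10/12 = 83.3%.
- Events and censoring both to last follow-up: 20 at risk, 2 events. 18/20 = 90.0%.
- Events and censoring both on treatment: all 10 who stop are censored at week 48, with no events. 100%.

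The written rule lies below both consistent rules. It keeps the two failures but removes the eight patients who shared their off-treatment risk.

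**3. Size by simulation**

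The documents give no rates, so these are assumptions. Times are exponential: on-treatment event 5% per year, stopping while in response 10% or 25% per year, off-treatment progression or CML-related death 1-10% per year. The data cut is uniform between 1.5 and 3.5 years after first response. With 2,000,000 responders per row, Monte Carlo error is about 0.1 point or less. The on-treatment rule should give exp(-0.05 x 96/52) = 91.2% at week 96 and exp(-0.05 x 144/52) = 87.1% at week 144, and the simulation returns both. Shortfalls are in percentage points below the on-treatment rule and below the follow-up rule.

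| Stop/yr | Off-treatment events/yr | Wk 96 as written | Below on-treatment rule | Below follow-up rule | Wk 144 as written | Below on-treatment rule | Below follow-up rule |
|---|---|---|---|---|---|---|---|
| 10% | 1% | 91.0% | 0.2 | 0.8 | 86.7% | 0.4 | 1.6 |
| 10% | 3% | 90.7% | 0.5 | 0.8 | 86.0% | 1.0 | 1.7 |
| 25% | 3% | 89.9% | 1.3 | 2.0 | 84.0% | 3.0 | 4.4 |
| 25% | 5% | 89.1% | 2.1 | 2.1 | 82.2% | 4.8 | 4.9 |
| 25% | 6% | 88.7% | 2.5 | 2.1 | 81.4% | 5.7 | 5.1 |
| 25% | 10% | 87.3% | 3.9 | 2.3 | 78.2% | 8.9 | 5.7 |

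The written rule is below both consistent rules in every row.

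The nearest figure in the documents is in Section 1.1: 5-year progression-free and overall survival of 80% to 95% on TKIs generally. As a constant hazard that is -ln(0.95)/5 = 1.0% to -ln(0.80)/5 = 4.5% per year. It is not a third-line population, and Section 2.6 notes higher progression risk after two failed TKIs, so it is only a rough anchor for the 1-6% range.

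**The case against.** **The window may simply be unstated.** PFS and OS say in terms that follow-up counts, and the two durations do not. One could read that silence, together with on-treatment censoring, as confining events to treatment. Part of this stands: for progression, off-treatment inclusion follows from an unrestricted definition plus routine collection and is not spelled out. For CML-related death the follow-up period is explicit, although the definition sits in the section on stopping treatment. At the least, two programmers could derive different curves. A restriction in a detailed SAP derivation would settle the matter; the protocol sections cited here contain none.

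**It is small against sampling error.** With an illustrative 70 responders and 88% still responding, the standard error is at least sqrt(0.88 x 0.12/70) = 3.9 points, a 95% interval of about +/-8. At the planning rate there would be about 0.15 x 74 = 11 bosutinib responders at week 24. This stands as a limit on importance. It does not excuse a systematic error that one sentence removes.

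**Stronger readings.** A reader might infer that the curves also absorb the effect of asciminib in bosutinib patients who switch. The documents do not support that: Section 4.1 has switch data analysed separately, and the Amendment 3 rationale keeps post-switch efficacy data out of the secondary endpoints. That exclusion does not reach responders who stop for other reasons. A reader might also infer a shortfall of 13 to 20 points. Figures that large need 40% per year stopping while in MMR and 10% per year off-treatment events, and nothing in the documents suggests such rates. Nor do the documents show that the arms will stop at different rates while in response, so a distorted comparison between arms is possible but not established.

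**Conclusion.** The point holds. As written, the event window and the censoring window differ for both durations, risk-set membership depends on later events, and the estimated rates of continued response are biased downward. The direction follows from the rule. The size depends on assumed rates: about 0.2 to 2.5 points at week 96 and 0.4 to 6 points at week 144 for stopping of 10-25% per year and off-treatment events of 1-6% per year, measured against an on-treatment rule and given 5% per year on-treatment events. It is larger only at more extreme rates. Both endpoints are exploratory; the primary test at week 24, the key secondary test at week 96 and the sample size are untouched.

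**What to change.** In Section 10.5.2, with a matching clause in Section 7.2.1.1, state that loss of response, progression to AP/BC or CML-related death counts as an event for these two durations only if it occurs on randomised treatment, up to the end-of-treatment assessment. All other patients are censored at the last on-treatment PCR (for CCyR, the last on-treatment cytogenetic assessment or PCR indicating MMR), regardless of later events.

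If a post-dose window is preferred, such as the 30 days used for safety in Section 10.5.3.1, event-free patients' follow-up for progression and death should run to the same limit; otherwise a small version of the asymmetry remains. Extending censoring to last follow-up would also be consistent for progression and death. It is the weaker choice, because PCR ends with treatment and an unobserved loss of MMR would count as continued response.

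The cost is a sentence per endpoint and one line of derivation code, with no new data. A few late progressions and deaths leave these endpoints but remain in PFS and OS.

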The cut-off date for the primary analysis is defined as the date when all patients have been on study treatment for 24 weeks or discontinued earlier. The cut-off date for the end of study treatment analysis is defined as 30 days after the end of study treatment period (see [Section 4.3](#)) to ensure that all available treatment phase data from all patients up to the last dose of study drug taken in this study, will be analyzed and summarized in the end of study treatment phase CSR. Patients will be further followed for survival and progression for up to 5 years from the date the last randomized patient receives the first study dose. An update analysis of OS and PFS will be performed at the end of the follow-up period in the final study CSR.

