10.1.6 Other analysis set

For duration of MMR and time to MMR, the MMR Responder Set that will be used is a subset of FAS and includes patients who achieve MMR at any time.

For CCyR rates at and by scheduled time points, the CCyR Analysis Set that will be used is a subset of FAS and includes patients who are not in CCyR at baseline.

For duration of CCyR and time to CCyR, the Cytogenetic Responder Set that will be used is a subset of FAS and includes patients who do not have CCyR at baseline and achieve CCyR at any time on study treatment.

Patients who will receive at least one dose of asciminib after bosutinib failure will form the Switch Analysis Set which will be used for safety and exploratory efficacy endpoints defined on these patients.

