The cumulative incidence of MMR will be graphically displayed by an increasing step function. This curve will increase each time (after randomization) at which a new responder is observed and thus will increase up to the best observed response rate (e.g. up to 50% if half of the patients in the analysis population are able to achieve response).

Time to MMR is defined in [Section 7.2.1.1](#) and calculated as: date of first MMR - date of randomization +1, for patients in the Molecular Responder Set. Descriptive statistics (minimum, maximum, median, quartiles, mean, sd) of time to MMR will be provided for the two treatment groups separately.

Cytogenetic Response

Patients in FAS will be categorized with counts and percentages provided for cytogenetic response (Complete, Partial, Major, Minor, Minimal, No Response) at and by (i.e. best response up to a specified time point) scheduled time points. Shift tables will also be employed to examine the changes in cytogenetic response category from baseline.

Since there are expected to be only limited numbers who are actually in CCyR at baseline the analysis of CCyR rate at and by scheduled time points will only include patients who are not in CCyR at baseline, i.e. the CCyR Analysis Set.

CCyR rates at and by scheduled time points etc. and the associated 95% confidence intervals based on the Pearson-Clopper method will be presented by treatment group with the analysis of these endpoints only including patients who are not in CCyR at baseline.

Confidence intervals for the differences in any response rates between treatment groups will be provided using the Wald method.

Statistical testing will be performed via CMH chi-square tests stratified by the randomization strata. The Mantel-Haenszel estimate of the common risk difference and the corresponding 95% confidence interval will also be provided.

Time to CCyR is defined for patients in the Cytogenetic Responder Set as: date of first CCyR - date of randomization +1. Descriptive statistics (minimum, maximum, median, quartiles, mean, sd) of time to CCyR will be provided for the two treatment groups separately.

The cumulative incidence of CCyR will also be graphically displayed by an increasing step function. This curve will increase each time (after randomization) at which a new responder is observed and thus will increase up to the best observed response rate.

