10.8 Sample size calculation

To test the null hypothesis that the response rate is equal in the two groups, based on two-sided 5% level of significance and with 90% power, 222 patients will be needed in total (i.e. 148 patients in the asciminib arm and 74 patients in the bosutinib arm based on 2:1 randomization allocation). This assumes that asciminib leads to a 20% improvement in the MMR rate at 24 weeks over bosutinib from 15% to 35% which corresponds to an odds ratio of 3.05.

The assumed bosutinib MMR rate of 15% at 24 weeks is based on previous trials evaluating bosutinib therapy ([Khoury 2012](#), [Gambacorti-Passerini 2014](#), [García-Gutiérrez 2015](#)).

No more than 66 patients (approximately 30% of the overall trial population) that are intolerant to their most recent TKI therapy with BCR-ABL1 < 1% will be recruited in order to ensure that the CML third line patient population is adequately represented.

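### Time to MMR and time to CCyR are summarised only among responders, and the companion incidence curve has no censoring beyond the common follow-up

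*Combined protocol and SAP*

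**What the plan says.** Time to MMR and time to CCyR appear in Section 10.5 and Table 3-1 under the aim of comparing further efficacy parameters between the arms. For most secondary endpoints Section 10.5.2 uses the Full Analysis Set (FAS), but it carves these out: "The exceptions are using the Molecular Responder Set for duration of MMR and time to MMR". Section 10.1.6 defines the MMR set as a subset of the FAS that "includes patients who achieve MMR at any time". The corresponding CCyR set takes patients without CCyR at baseline who reach it while on study treatment.

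The analysis of time to MMR is then: "Descriptive statistics (minimum, maximum, median, quartiles, mean, sd) of time to MMR will be provided for the two treatment groups separately". Time to CCyR is handled in the same way. Neither has a censoring rule, a between-arm estimate or a confidence interval.

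Section 10.5.2 also plans a cumulative-incidence plot. It steps up with each new responder "and thus will increase up to the best observed response rate", illustrated by a curve that ends at 50% when half the analysis population responds. The denominator therefore includes non-responders. Its population is not named and no censoring is described.

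On timing, Section 10 states: "The cut-off date for the primary analysis is defined as the date when all patients have been on study treatment for 24 weeks", or have discontinued sooner. Under Section 4.3 the treatment period runs at least to 96 weeks after the last patient's first dose.

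**The concern.** A median among responders depends on who responds as well as how fast. A drug that converts extra patients later adds late times to its own summary and can look slower than a drug that never converts them. Randomisation does not protect a comparison of two groups selected by the outcome. Because these are named comparative endpoints, the two medians are likely to be read side by side as showing which drug acts sooner.

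The curve has a separate and narrower problem. It is the number of responders divided by everyone. Once it runs past the time to which all patients could have been followed, someone randomised too recently to have reached that week is counted as not having responded by then. Section 10.5.2 does give censoring rules for duration of MMR, time to treatment failure, PFS and OS, so the gap is specific to these two endpoints.

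**Working it through.** **The plan's own figure.** The documents give no figure for time to MMR. The rates used below come from Section 10.8: "based on two-sided 5% level of significance and with 90% power, 222 patients will be needed in total", for 15% v 35% at 2:1. With p̄ = (0.15 + 2 × 0.35)/3 = 0.2833 and pooled variance,

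n(bosutinib) = [1.960 √(1.5 × 0.2833 × 0.7167) + 1.282 √(0.15 × 0.85 + 0.35 × 0.65/2)]² / 0.20² = 73.2, rounded up to 74.

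The total is 3 × 74 = 222, which reproduces, with power 90.3%.

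**Responder-only summary, constant hazards (assumed).**

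- Hazards per week: asciminib −ln(0.65)/24 = 0.01795; bosutinib −ln(0.85)/24 = 0.00677. Ratio 2.65.
- Median among responders by week T: −ln(1 − F(T)/2)/λ.
- At T = 24: asciminib −ln(0.825)/0.01795 = 10.7 weeks; bosutinib −ln(0.925)/0.00677 = 11.5 weeks. The means are 11.1 and 11.7.
- At T = 96 the same formula gives 29.5 v 40.3 weeks. The summary changes with the length of follow-up while the true ratio stays at 2.65.

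**Can the direction reverse?** Invented counts of first MMR at Weeks 4, 8, 12, 16 and 24, keeping about 35% and 15%:

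- Asciminib 6, 9, 12, 11, 14 (52/148). Cumulative 4.1, 10.1, 18.2, 25.7, 35.1%.
- Bosutinib 2, 3, 3, 2, 1 (11/74). Cumulative 2.7, 6.8, 10.8, 13.5, 14.9%.

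Asciminib leads at every visit. Both responder medians are 12 weeks, and the responder mean is later for asciminib: 752/52 = 14.5 v 124/11 = 11.3 weeks. This shows that reversal is possible, not that it is likely.

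**Follow-up at the primary cut-off.** The amendment rationales give 38 randomised by 29-Jun-2018, 86 by 21-Nov-2018 and 233 in total, with recruitment complete on 22-Oct-2019. Cut-off 24 weeks later is about 7-Apr-2020. Let B be the weeks from a patient's randomisation to the end of recruitment, so potential follow-up is 24 + B. With even accrual inside each interval (assumed):

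- 147 patients: B uniform on 0 to 47.9, mean 23.9.
- 48 patients: B uniform on 47.9 to 68.6, mean 58.2.
- 38 patients: B above 68.6, spread back to an assumed first entry in late October 2017.

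About 32% have under 48 weeks and 63% under 72 weeks; only about 15% have 96.

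**Crude curve, linear growth (assumed).** Let asciminib rise from 35% at Week 24 to 53% at Week 96, and bosutinib from 15% to 30%. The crude curve at week w is F(24) + slope × E[min(w − 24, B)], with slopes 0.18/72 = 0.00250 and 0.15/72 = 0.00208 per week.

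| Week | E[min(w − 24, B)] | Asciminib crude v true | Bosutinib crude v true |
|---|---|---|---|
| 24 | 0 | 35.0 v 35.0 | 15.0 v 15.0 |
| 48 | 20.2 | 40.1 v 41.0 | 19.2 v 20.0 |
| 72 | 32.8 | 43.2 v 47.0 | 21.8 v 25.0 |
| 96 | 38.8 | 44.7 v 53.0 | 23.1 v 30.0 |

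For example, at Week 96: (147 × 23.9 + 48 × 58.2 + 38 × 71.8)/233 = 38.8. The assumed first-entry date hardly matters: for the last 38 patients the capped value lies between 68.6 and 72, which gives 44.6% to 44.7%.

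As a steeper alternative, constant hazards give 54.4 v 57.8 at Week 48 and 62.4 v 72.5 at Week 72 on asciminib, and 25.8 v 27.8 and 31.5 v 38.6 on bosutinib.

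**The case against.** The strongest reply is that the plan already looks at timing in all randomised patients. Section 10.5.2 gives the MMR rate by every scheduled visit, by default on the FAS, with exact intervals per arm, Wald intervals for the difference and a stratified Mantel-Haenszel risk difference. PCR is scheduled at Weeks 4, 8, 12, 16, 24, 36 and 48 and every 12 weeks after that (Table 7-3). A reader might infer that nothing in the plan shows which drug works sooner. The documents do not support that: these rates show which arm has more responders by each visit, and so does the curve within common follow-up.

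The curve can also be defended. No patient still on treatment has under 24 weeks at the primary cut-off, or under 96 weeks of potential follow-up at the end of the treatment period. Inside those windows, keeping patients who discontinue in the denominator is ordinary competing-event handling. Section 10.7 describes the other efficacy analyses at the primary report as those at and by Week 24. The shortfall also affects both arms: at Week 96 the crude gap is 44.7 − 23.1 = 21.6 points against a true 23.0. All of this stands. What remains is a plot with no stated end point and no censoring rule.

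A reader might also infer that bosutinib patients who reach MMR after switching to asciminib will be counted as bosutinib responders, because the MMR set has no treatment limit. Section 4.1 says efficacy data from switching patients are analysed separately, and Sections 10.1.6 and 10.6.1.1 provide a Switch Analysis Set for them. The set definition needs a phrase to agree with that; contamination is not planned.

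Finally, Section 10.5.2 calls these analyses exploratory and plans no test on them. That lowers the stakes but does not make an outcome-selected summary a fair comparison.

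**Conclusion.** The responder-only summaries of time to MMR and time to CCyR do not compare the randomised arms, and can hide or reverse a difference in speed. At Week 24, under the plan's rates and assumed constant hazards, a 2.65-fold ratio shows as less than one week (10.7 v 11.5). The reversal rests on invented counts.

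The curve is sound up to the minimum common follow-up. Beyond Week 24 at the primary cut-off it reads low: about 1 point at Week 48, 4 at Week 72 and 8 at Week 96 on asciminib, and 7 at Week 96 on bosutinib. These figures assume piecewise-even accrual and linear growth. The 53% is the effect detectable with 90% power in Table 10-2, not an expected rate, and all four rates are defined at a visit rather than cumulatively. The sizes are therefore illustrative.

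The primary and key secondary tests and the sample size are unaffected. The change is worth making because the endpoints are named as comparative and a better estimate needs no new data.

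**What to change.** In Section 10.5.2:

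- Estimate time to first MMR on randomised treatment in the FAS with the cumulative incidence function (Aalen-Johansen).
- Treat discontinuation of randomised treatment, progression, or death without MMR as competing events. Censor patients still on randomised treatment without MMR at their last PCR.
- Report estimates with 95% confidence intervals by arm at Weeks 24, 48 and 96, where follow-up allows. Use this function for the plot and name its population.
- Keep the responder-only statistics, labelled as descriptive and not for comparing the arms.

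Do the same for time to CCyR in the CCyR Analysis Set, censoring at the last cytogenetic assessment. Because Section 7.2.1.2 drops the scheduled on-treatment marrow samples once MMR is reached, the SAP should also say how a patient in MMR with no documented CCyR is counted.

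In Section 10.1.6, limit both responder sets to response on randomised treatment so that they agree with Section 4.1. Use one name for the MMR set, which is the MMR Responder Set there and the Molecular Responder Set in Section 10.5.2.

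The cost is SAP wording and a little extra analysis on data already collected.
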